#### ECG Findings That May Qualify as SAEs

- QTcF prolongation >500 ms.
- Absolute value of QTcF >450 ms AND QTcF change from baseline >60 ms.
- New ST-T changes suggestive of myocardial ischemia.
- New-onset LBBB (QRS complex >120 ms).
- New-onset right bundle branch block (QRS complex >120 ms).
- Symptomatic bradycardia.
- Asystole
  - In awake, symptom-free subjects in sinus rhythm, with documented asystolic pauses ≥3 seconds or any escape rate <40 bpm, or with an escape rhythm that is below the AV node;
  - In awake, symptom-free subjects with atrial fibrillation and bradycardia with 1 or more asystolic pauses of at least 5 seconds or longer.
- Atrial flutter or fibrillation, with rapid ventricular response rate: rapid = rate >120 bpm.
- Sustained supraventricular tachycardia (rate >120 bpm) ("sustained" = short duration with relevant symptoms or lasting >1 minute).
- Ventricular rhythms >30 second duration, including idioventricular rhythm (HR <40 bpm), accelerated idioventricular rhythm (HR 40 bpm to <100 bpm), and monomorphic/polymorphic ventricular tachycardia (HR >100 bpm [such as torsades de pointes]).
- Type II second-degree (Mobitz II) AV block.
- Complete (third-degree) heart block.

# ECG Findings That Qualify as SAEs

- Change in pattern suggestive of new myocardial infarction.
- Sustained ventricular tachyarrhythmias (>30-second duration).
- Second- or third-degree AV block requiring pacemaker placement.
- Asystolic pauses requiring pacemaker placement.
- Atrial flutter or fibrillation with rapid ventricular response requiring cardioversion.
- Ventricular fibrillation/flutter.
- At the discretion of the investigator, any arrhythmia classified as an adverse experience.

The major events of potential clinical concern listed above are recommended as "alerts" or notifications from the core ECG laboratory to the investigator and Pfizer study team, and not to be considered as all-inclusive of what is to be reported as AEs/SAEs.

Version Number	Brief Description Summary of Changes	Date
Version 1.0 – Original	Not Applicable	04-Apr-2022
	• Updated Section 4.3, Schedule of Assessments: history of triptan use and CV risk factors added	
	• Updated Section 5.2, Inclusion Criteria: inclusion criteria 2g clarified.	30-Aug-2022
Version 2.0	• Updated Section 5.3, Exclusion Criteria: exclusion criteria 1a reworded.	
	• Updated Section 5.4, Prohibited and Restricted Concomitant Medications: Traditional Chinese Medicines and Lasmiditan added.	
	• Corrected inconsistencies and typographical errors throughout the protocol.	
	• Updated Section 5.2, Inclusion Criteria: inclusion criteria 2g modified.	
	• Updated Section 5.3, Exclusion Criteria: exclusion criteria 1a, 1b, 2i, 2n, 5f, 5g and 5i modified.	
	• Updated Section 5.4, Prohibited and Restricted Concomitant Medications: #8,9 and 18 modified.	
Version 3.0	• Updated Section 5.5, Rescue Medications: Revision to upper limit of acetaminophen dose from 1000 mg/day to 2000 mg/day.	27-Feb-2023
	• Updated Section 8.1.2, Collection and Reporting Serious Adverse Events: immediate notification to the Medical Monitor no longer required.	
	• Provided clarifications throughout the protocol.	
	• Corrected inconsistencies and typographical errors throughout the protocol.	

	Section 6.1.1.1: Add "DB or OL Rimegepant" treatment group for the follow-up safety analysis set.
	Section 6.2.1: Modified the administrative listing of randomization scheme and codes.
	Section 6.2.3.3: Specified that summary of "continued to the next phase" and "did not continue to the next phase" is shown by subcategories of complete status of DBT phase.
	Section 6.2.4: Added the by-subject listing of significant protocol deviations. Changed the analysis set to be used for the by-subject listing.
	Section 6.2.5: Added the cross-tabulation of the number and percentage of subjects in each randomization stratum from IWRS and those from actual data.
	Section 6.2.5.1: Removed the OL rimegepant baseline and DB or OL rimegepant baseline.
	Section 6.2.5.4: Deleted the frequency tables of migraine standard of care for non-study prior medications.
	Section 6.2.6.1: Removed the administrative listing of IP batch numbers. Modified the formula used in the calculation of the average OL rimegepant exposure (tablets per month) and average DB or OL rimegepant exposure (tablets per month). Removed the average OL Rimegepant exposure (tablets per month) categories from parameters for OL rimegepant exposure.
	Section 6.2.6.2: Changed "< 80%" to " \geq 80%" for DB tablet and OL rimegepant tablet count compliance. Added the category of "OL Rimegepant taken during the DBT phase" for DB treatment compliance and category of "DB study drug never taken" for OL rimegepant treatment compliance, respectively. Change the analysis set used for the table of eDiary usage compliance.
	Section 6.3: Specified to use randomization stratum based on actual data, not IWRS. Added detail on the by-subject listing of primary and secondary efficacy endpoints.

Section 6.3.1.1: Changed the analysis set for the frequency table of missing efficacy data in the OP and DBT phase. SE estimation method in the linear mixed effects model for the main analysis was changed to use Huber-White robust "sandwich" estimator. Added subgroup analyses by chronic migraine according to ICHD 3rd edition. For the J2R macros, edited the description on the Ndraw and thin parameters.

Section 6.3.2.1: Specified that Mantel-Haenszel risk estimation will be used in the analyses for percentages of subjects with reduction in migraine days per month in the DBT phase. Added subgroup analyses by chronic migraine according to ICHD 3rd edition.

Section 6.3.2.2: Same changes with Section 6.3.1.1 (i.e., main analysis for the primary endpoint) are made on the model analyses. Added subgroup analyses by chronic migraine according to ICHD 3rd edition.

Section 6.3.3: Same changes with Section 6.3.1.1 and section 6.3.2.1 are made on the linear mixed effects model and binary endpoint analyses, respectively.

Section 6.3.3.5: Modified the formula for the medication days per month on planned scheduled OL rimegepant dosing/ planned non-scheduled OL rimegepant dosing days through Month 10.

Section 6.4: Removed the pretreatment safety analysis period. Removed following sections: Pretreatment AEs, Post DBT pre-OL rimegepant AEs, and AEs across all study phases combined.

Section 6.4.1: The definition of AE relatedness is specified in the study SAP. Changed "by intensity" to "by worst intensity".

Section 6.4.1.2: Added SAE related to study drug to AE overview frequency table.

Section 6.4.1.3: Removed following AE frequency tables: medication-overuse headache AEs, and exposure-adjusted multiple occurrences of unique AEs.

Section 6.4.1.4: Added following AE frequency tables: hepatic-related AEs, hepatic-related AEs leading to study drug discontinuation, potential drug abuse AEs, cardiovascular AEs, and suicidality AEs.

Section 6.4.1.5: Specified the AE frequency tables: AEs by worst intensity, SAEs, and exposure-adjusted multiple occurrences of unique AEs.

Section 6.4.2: Specified the laboratory test criteria used for toxicity grading.

Section 6.4.2.1: Removed laboratory test worst abnormalities tables for interim analysis set and DB or OL Rimegepant analysis set. Changed the analysis set for laboratory test shift from baseline to the worst abnormality for each graded laboratory test from DB or OL rimegepant safety analysis set to OL rimegepant safety analysis set.

Section 6.4.2.2: Removed frequency table of LFT elevations for pretreatment safety analysis period. Changed the analysis set for frequency tables of LFT shifts from baseline to worst elevation and eDISH plot from DB or OL rimegepant safety analysis set to OL rimegepant safety analysis set. Removed the tables of exposure-adjusted cumulative LFT elevations and time to first LFT elevation for DBT safety analysis set.

Sections 6.4.2.3, 6.4.3.1, and 6.4.4.1: Removed the changes from baseline table using DB or OL Rimegepant baseline for laboratory test, vital sign and physical measurement, and ECG.

Sections 6.4.3.2 and 6.4.4.2: Changed the analysis set from DB or OL rimegepant safety analysis set to OL rimegepant safety analysis set for frequency tables of vital sign and physical measurement abnormalities and ECG abnormalities.

Section 6.4.5: Changed the analysis set from DB or OL rimegepant safety analysis set to OL rimegepant safety analysis set for frequency table of C-SSRS suicidality.

Section 6.4.6: Modified the event of special interest provided in the safety narrative

subject identifiers.

Section 6.5 Removed the results in EOT from the tables for outcomes research endpoints. SE estimation method in the linear regression model is changed to use Huber-White robust "sandwich" estimator.

Section 7.2: Removed pre-OL rimegepant and Pre-DB or OL Rimegepant safety analysis periods. Modified the purpose of the pretreatment analysis period.

Section 7.3: Modified the analysis visit window for "screening" and "prerandomization". Removed the description on the DB or OL Rimegepant safety analysis period to define analysis visit windows.

Section 8: Modified the content of analyses for each report.

Section 9.1: Changed "more than once and assigned" to "under". Removed subcategories for cardiovascular disease risk factor. Modified the subcategories for medical history. Modified the subcategory of headache days for the efficacy data issue. Modified the description on the prohibited non-study medications.

Section 9.2.3: Changed the definition of acute migraine medication day.

Section 9.3: Modified the SAS codes in accordance with the change in the analysis defined in sections 6.3.1.1 and 6.5.1.

Abbreviation	Definition
AE	Adverse event
ALP	Alkaline phosphatase
ALT	Alanine aminotransferase
ASE	Asymptotic standard error
AST	Aspartate aminotransferase
BMI	Body mass index
CGRP	Calcitonin gene-related peptide
CI	Confidence interval
CRF	Case report form
CSR	Clinical study report
DB	Double-blind
DBT	Double-blind treatment
eDiary	Electronic diary
eDISH	Evaluation of drug-induced serious hepatotoxicity
eGFR	Estimated glomerular filtration rate
EOD	Every other day
EQ-5D-5L	EuroQol 5 Dimensions 5 Levels
FCS	Fully conditional specification
GLM	Generalized linear model
GLMEM	Generalized linear mixed effect model
IP	Investigational product
IWRS	Interactive web response system
LFT	Liver function test
LSM	Least-squares mean
MDRD	Modification of diet in renal disease
MSQoL	Migraine Specific Quality of Life
ODT	Orally disintegrating tablet
OL	Open-label
OLE	Open-label extension
PCD	Primary completion date
P-gp	Permeability glycoprotein
PRN	Pro re nata

РТ	Preferred term
SAE	Serious adverse event
SAP	Statistical analysis plan
SE	Standard error
SI	Systeme Internationale
SOC	System organ class
TBL	Total bilirubin
TLF	Table listing figure
ULN	Upper limit of normal
VAS	Visual analog scale

_

1 BACKGROUND AND RATIONALE

This document presents the statistical analysis plan (SAP) for Protocol C4951021: A Phase 3 Randomized, Double-blind, Placebo-Controlled Study to Evaluate the Efficacy and Safety of Rimegepant for Migraine Prevention in Japanese Subjects.

This SAP contains the analysis details and methodology to answer the study objectives, including planned tables, listings, and figures (TLFs), which provide the basis for the results section of the clinical study report (CSR).

This SAP also references the Rimegepant/Zavegepant Core SAP, which is hereafter referred to as the "Core SAP".

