#### **Regulatory Agency Identification Number(s):**

US IND Number:	NA
EudraCT Number:	NA
ClinicalTrials.gov ID:	NCT05399459
Pediatric Investigational Plan Number:	NA
Protocol Number:	BHV3000-313 (C4951022) Version 4.0
Phase:	2/3

**Rationale:** Rimegepant is being developed for the treatment of migraine. Effectiveness as an acute treatment for migraine was demonstrated in a Phase 2b double-blind, randomized, placebocontrolled, dose-ranging study that compared rimegepant at doses of 10, 25, 75, 150, 300 and 600 mg to placebo (CN170003 study). In this study, rimegepant at 75 mg showed efficacy on all 4 traditional endpoints: pain, nausea, photophobia and phonophobia. The primary endpoint was pain freedom at 2 hours post-dose. In this study the 10 and 25 mg doses did not separate from placebo. The 75, 150 and 300 mg doses were significantly better than placebo and showed similar efficacy. The efficacy of the 600 mg dose was somewhat less than that of the 75, 150 and 300 mg doses, but was still better than that of placebo.

In the United States, the 75 mg dose was selected as the optimal dose and tested against placebo in 3 pivotal studies for the acute treatment of migraine. The efficacy of the 75 mg dose was confirmed in all 3 studies.

This study is being conducted to determine the appropriate dose of rimegepant in Japanese subjects, as well as to evaluate the efficacy, safety, and tolerability of rimegepant in Japanese subjects for the acute treatment of migraine.

Since the optimal dose in the US has been demonstrated to be 75 mg and the 25 mg dose is included in the study to permit an assessment of the dose response for rimegepant in Japanese subjects, formal hypothesis testing compared with placebo will be restricted to rimegepant 75 mg arm.

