- Freedom from nausea at 2 hours post-dose will be assessed using the percentage of subjects with nausea absent at 2 hours post-dose in the subset of subjects with nausea present at the time of dosing.
- Pain relapse from 2 to 48 hours post-dose will be assessed using the percentage of subjects with a pain intensity of mild, moderate, or severe at any time point after 2 hours through 48 hours post-dose in the subset of subjects with pain freedom at 2 hours post-dose.
- Tolerability and safety will be evaluated by the percentage of subjects with AEs by intensity, SAEs, and grade 3 to 4 laboratory test abnormalities.

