#### Study BHV3000-313 (C4951022) Clinical Protocol, Version 4.0 BHV-3000 (PF-07899801) (rimegepant)

				End of				
Procedure	Screening Visit (3-28 days) 	Baseline Visit (Randomization) 	Onset of moderate or severe migraine 	15, 30, 45, 60 and 90 minutes Post-Dose	2, 3, 4, 6, 8 hours Post- Dose	24 hours Post-Dose	48 hours Post- Dose	Treatment Visit (within 7 days of treatment) 
Safety Assessments								
Physical Examination	X							X
Vital Signs/ Physical Measurements 	X	Х						X
Clinical Safety Laboratory Testing	X 							X
Urine drug screen for drugs of abuse	Х							X
ECG	X							X
Pregnancy Test 	X (serum)	X (urine)	X (urine)					X (serum)
Adverse Event and Serious Adverse Event Assessment 	X	X	X	Х	X	X	X	X
Columbia-Suicide Severity Rating Scale (C-SSRS) 	X	X						X

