-  These scales will be captured in the eDiary. Subjects will also be asked about their most bothersome symptom at the time of reporting and treating a qualifying migraine.
-  Subjects should return to the site for their EOT visit within 7 (+4) days of study drug dosing.

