#### 9.3.5. Analysis of Safety

The investigators will determine the intensity of AEs and the relationship of AEs to study therapy. The investigators' terms will be coded and grouped by system organ class using the latest version of the Medical Dictionary for Regulatory Activities (MedDRA) available. AEs will be presented by system organ class and preferred term. In tables by intensity, if a subject had an AE with different intensities over time, then only the greatest intensity will be reported. In tables by relationship to study drug, if a subject has an AE with different relationships over time, then the highest degree of relatedness to study drug will be reported.

Deaths will be listed for the enrolled analysis set without regard to onset.

The frequencies of the following on-treatment safety events and findings will be summarized by treatment group for the safety analysis set: SAEs; AEs by intensity; AEs by relationship to study drug; laboratory test abnormalities by toxicity grade; and liver function test elevations based on fold changes above the upper limit of normal.

Laboratory test results will be graded according to numeric laboratory test criteria in Common Terminology Criteria for Adverse Events (CTCAE) Version 5.0 (2017), if available. Otherwise, if CTCAE grades are not available, then results will be graded according to numeric laboratory test criteria in Division of AIDS (DAIDS) Table for Grading the Severity of Adult and Pediatric Adverse Events Corrected Version 2.1 (2017). If a subject has a laboratory test abnormality with different toxicity grades over time, then only the highest toxicity grade will be reported.

Further safety analyses will be described in the SAP.

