2.4 Protocol and Protocol Amendments

C4951021 SAP Version 1 is based on C4951021 Protocol Version 4 (27-Feb-2023).

C4951021 SAP Version 2 is based on C4951021 Protocol Version 5 (04-Aug-2023). Protocol changes that affected statistical analyses were the following: changing the sponsorship to Pfizer; stating that there are 3 planned database locks and 3 final CSRs; using robust standard error (SE) estimation methods; excluding subject as a random effect from linear mixed effects models; and replacing Cochran-Mantel-Haenszel test with Mantel-Haenszel risk estimation.

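### Does filing the C4951021 SAP with Protocol C4951022 leave this trial without a usable analysis plan or an on-treatment safety window?

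*SAP*

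**What the plan says.** The protocol identifies itself as "BHV3000-313 (C4951022) Version 4.0". The SAP's opening section reads "This document presents the statistical analysis plan (SAP) for Protocol C4951021: A Phase 3 Randomized, Double-blind, Placebo-Controlled Study", and its Section 2.4 ties it to Version 5 of the C4951021 protocol.

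Protocol Section 9 leaves three things to its SAP: full statistical detail, the sensitivity analyses of the primary endpoint (Section 9.3.2), and further safety work, where Section 9.3.5 says "Further safety analyses will be described in the SAP".

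The safety endpoint in Protocol Section 3.2 is: "Tolerability and safety will be evaluated by the percentage of subjects with AEs by intensity, SAEs, and grade 3 to 4 laboratory test abnormalities". Section 9.3.5 then says "The frequencies of the following on-treatment safety events and findings will be summarized by treatment group for the safety analysis set". The protocol does not define *on-treatment*. In Table 1 the row "Clinical Safety Laboratory Testing" is marked only at Screening and at the End of Treatment Visit. Footnote 15 states: "Subjects should return to the site for their EOT visit within 7 (+4) days of study drug dosing". Section 4.3.4 gives the same window, while Section 4.1 and the Table 1 column heading mention seven days alone.

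**The concern.** The mismatch is in body text, so it cannot come from a stripped title page. Anyone who follows the protocol's references to its SAP arrives at a plan for a different design. The deferred sensitivity and safety analyses of C4951022 therefore cannot be checked from these two documents.

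The laboratory endpoint makes this look concrete. A treated subject has one scheduled post-dose safety draw. SAP Section 3.2 keeps safety data up to seven days after study drug stops. The draw may fall up to eleven days after dosing. If the two were combined, a subject seen late but within the permitted window would have no on-treatment laboratory value, and adverse events starting on those days would go uncounted. A rule running from dosing to the End of Treatment Visit would count everything. The same data would then give two sets of denominators for a listed secondary safety endpoint.

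The start of the window is unstated too: the protocol's Treatment Phase includes a wait of up to 45 days before dosing.

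**Working it through.** **1. Is the SAP misfiled, or a faulty plan for this trial?**

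| | Protocol C4951022 | SAP on file |
|---|---|---|
| Indication | acute treatment | prevention |
| Dosing | one dose | every other day for up to 12 weeks, then open-label extension |
| Arms | 25 mg, 75 mg, placebo | 75 mg, placebo |
| Randomized | about 795 | about 490 |
| Primary endpoint | pain freedom at 2 hours | change in monthly migraine days |

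Nothing overlaps except the drug, the country and the stratification factor. The SAP is coherent for its own trial. With 225 per arm, a difference of 1 day and an SD of 3.75, power = Φ(1 / (3.75 × √(2/225)) − 1.96) = Φ(2.828 − 1.96) = 80.7%, against its stated 80% or so. It is the right plan for another study.

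**2. Does the protocol stand without it?** Its sizing figure can be reproduced from Section 9.1 alone: 10.9% versus 21.2%, 250 per arm, two-sided alpha 0.025.
- Pooled rate 0.1605; null SE = √(2 × 0.1605 × 0.8395 / 250) = 0.03283.
- Alternative SE = √((0.109 × 0.891 + 0.212 × 0.788) / 250) = 0.03251.
- Power = Φ((0.103 − 2.241 × 0.03283) / 0.03251) = Φ(0.905) = 81.7%, against the stated 80%. At the Version 4.0 alpha of 0.05 it is 88.3%.

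The remaining essentials are also in the protocol: analysis sets (9.2); stratified Mantel-Haenszel estimate, alpha and missing-as-failure (9.3.2); rescue use as failure (Section 3, 9.3.2, 9.3.3); the rule for multi-time-point endpoints (9.3.3); fixed testing order (9.3.4, with the order in Section 2); and safety tables with grading criteria (9.3.5).

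**3. Is there a matching SAP?** The Version 4.0 amendment summary says that the analysis sets, statistical methods and safety analysis sections were aligned with the Statistical Analysis Plan. The C4951021 SAP has no two-hour endpoints and no 25 mg arm, so it cannot be the document meant. A C4951022 SAP, at least in draft, is the natural inference.

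**4. The window arithmetic.** Latest draw under footnote 15: 7 + 4 = 11 days after dosing. Under a borrowed cut-off of 7 days, days 8, 9, 10 and 11 fall outside, which is 4 of 11 permitted days. That fraction is not a share of subjects, and the documents give no such share.

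**5. Size if the borrowed rule were used.** Take 250 per arm. This is the efficacy set; the safety set requires only intake, so it is at least as large. Upper 97.5% bound with zero events = 1 − 0.025^(1/n). Chance of at least one event at a true rate of 1% = 1 − 0.99^n.

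| Assumed share on days 8 to 11 | n left | Upper bound | Chance of ≥1 event |
|---|---|---|---|
| 0% | 250 | 1.46% | 91.9% |
| 10% | 225 | 1.63% | 89.6% |
| 20% | 200 | 1.83% | 86.6% |
| 40% | 150 | 2.43% | 77.9% |

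**6. Does any text apply that rule here?** No. SAP Section 7.2 takes its safety periods from Core SAP definitions for multiple-dose studies with double-blind and open-label phases, which this trial is not. Even in C4951021 the later values are not lost: Table 5 of that SAP assigns follow-up days 8 to 35 to a follow-up period, and its Section 6.4.2.1 tabulates worst laboratory abnormalities there.

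**7. Start of the window.** Scheduled safety laboratory tests occur only at Screening and End of Treatment, so starting at randomization or at dosing makes no difference to them. Only adverse events could be affected. The tables are restricted to subjects who took study drug, and the ordinary meaning of *on-treatment* starts at intake.

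**The case for a change.** The best argument for acting is that *on-treatment* decides which data enter a listed endpoint, that the protocol sends the reader to a SAP for detail, and that no document on file for this trial settles it. The collection periods in Sections 8.1.2 and 8.2.1 do not settle it either. They govern what is collected, not what is tabulated, and they start at consent for serious events and at Baseline for non-serious ones, so a window from intake through End of Treatment would agree with them only at its end. A sponsor might also carry a seven-day convention from one rimegepant trial to the next, and one clarifying sentence would be cheap.

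The identity mismatch stands, and so does the limit on checking the deferred analyses. The harm does not stand. It requires treating the C4951021 SAP as foreign to this trial and then applying one of its rules to it. The endpoint definition in Section 3.2 carries no on-treatment limit; only the summary sentence in 9.3.5 does. Repeat and unscheduled tests are provided for in Section 6.2.4, so the scheduled draw need not be the only post-dose value. In a single-dose trial whose only scheduled post-dose laboratory visit is End of Treatment, an analyst has little reason to choose a window that cuts off part of that visit's permitted range.

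**Conclusion.** No change to the plan is called for. The wrong SAP in the file is a document-management slip. Supplying the right one would complete the record without altering what the trial does or concludes. The primary test, alpha, testing order and missing-data rule are in the protocol and are unaffected.

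What remains is an undefined term in descriptive safety tables, a gap that the trial's analysts would fill sensibly. Its size is hypothetical: an upper bound moving from 1.46% to at most 2.43%, and a detection chance falling from 91.9% to at worst 77.9%. Both depend on an assumed share of 10% to 40% and on a rule that no document applies to this trial.

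The conclusion rests on two assumptions: that the SAP named in the amendment summary exists, and that the window is set before unblinding. The differing statements of the End of Treatment window (Section 4.1 and the Table 1 heading against footnote 15 and Section 4.3.4) are clerical and must be reconciled as housekeeping. They do not affect the analysis.
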